6.3. Schematic Diagram

Figure 1 provides an overview of participant flow in the trial.

[figure not shown]

Figure 1. Flow Diagram for COMBAT

6.4. End of Study

For the purposes of submitting the end of trial notification to the Sponsor and the Research Ethics Committee (REC), the end of trial will be considered to be when database lock occurs. The trial will be stopped prematurely if:

- Mandated by the REC
- Mandated by the Sponsor (e.g. following recommendations from the DMEC and TSC)
- Funding for the trial ceases

The REC that originally gave a favourable opinion for the trial will be notified in writing when the trial has been concluded or if it is terminated early.

7. TRIAL SETTING AND PARTICIPANT ELIGIBILITY CRITERIA

7.1. Study Setting

Recruitment for COMBAT will take place in at least 30 hospital eye services (HES) across the four UK nations, with catchment areas that cover diverse populations. A list of study sites will be maintained in the TMF.

7.2. Eligibility Criteria

Eligibility for the trial will be confirmed by an ophthalmologist delegated to undertake this task on their site's delegation log. Patients will be eligible if they fulfil the following criteria:

Inclusion Criteria

- Adults >50 years of age
- Non-highly myopic (< -6 diopters; <26.5 mm axial length) phakic RRD
- Naïve to previous vitreoretinal surgery
- Pars plana vitrectomy is planned to repair their RRD.

Exclusion Criteria

- Presence of a "formed/established cataract".
 - A "formed/established cataract" is defined as a cataract that, based on the Age-Related Eye Disease Study (AREDS) Research Group (16), is graded as nuclear sclerosis of ≥ 3 and/or if there is an anterior cortical cataract and/or a subcapsular posterior cataract involving the visual axis.
- Pseudophakia or aphakia.
- High myopia (> -6 diopters; >26.5 mm axial length).
- Giant retinal tear (i.e. presence of one or more retinal tears of >3 clock hours in size).
- Retinal dialysis.
- Participation in an investigational drug study.
- Declined consent for participation.

7.3. Co-enrolment Guidelines

Participants enrolled in investigational drug studies are not candidates for this study. Participants enrolled in other studies can take part in COMBAT provided that their participation will not jeopardise their participation in COMBAT. Co-enrolment with other studies should be documented in the Case Report Form (CRF).

8. TRIAL TREATMENT

8.1. Trial Intervention and Comparator

Eligible patients will be offered participation in the COMBAT study. If they consent, they will be randomised (1:1) to the intervention or comparator group.

Intervention: Phacovitrectomy

Participants will undergo phacovitrectomy to remove the lens (phacoemulsification and intraocular lens implantation) and to repair the RRD (vitrectomy). Based on the BEAVRS database, most vitreoretinal surgeons in the UK are not currently undertaking combined phacovitrectomy for RRD. Phacovitrectomy, however, is common practice for other retinal disorders such as macular hole. Although a phacovitrectomy is done in the same manner whether the condition to be treated is macular hole or RRD, the calculations required for the surgeon to select which intraocular lens should be implanted are different if there is a RRD with a detached macula. For this reason, a Standard Operating Procedure (SOP) will be prepared for the phacovitrectomy group to guide surgeons on how to best determine the intraocular lens under these circumstances (17). Vitrectomy with any gauge size (e.g.23g, 25g, 27g) will be allowed for the surgery, as per standard care at the participating site. The choice of the tamponade agent will be at the discretion of the treating vitreoretinal surgeon, as per standard care.

Comparator: Vitrectomy (Standard Care)

Participants will receive vitrectomy to repair their RRD. The vitrectomy would be done as per standard care. Vitrectomy with any gauge size (e.g.23g, 25g, 27g) will be allowed for the surgery, as per standard care at the participating site. The choice of the tamponade agent will be at the discretion of the treating vitreoretinal surgeon, as per standard care. Then, if a cataract develops, phacoemulsification and intraocular lens implantation will be done as per standard clinical practice.

8.2. Rescue Treatment

In either randomised group, if the surgery fails to repair the RRD (i.e. if the retina remains detached or if it attaches but then re-detaches), further surgery is allowed as per standard clinical practice. The surgery will be done as per standard clinical practice. Similarly, if complications occur, these would be treated as per standard clinical practice.

8.3. Treatment Adherence

At all participating sites, investigators should ensure that participants receive the intervention allocated by the randomisation (phacovitrectomy or vitrectomy) and be followed-up until trial completion (i.e. 52 weeks (+/- 6 weeks) after surgery). Investigators and the research study team should do their best to retain all participants until trial completion.

8.4. Post-Trial Care

After participants have completed the trial, arrangements for their future care will be as per standard practice within the NHS.

9. ASSIGNMENT OF TREATMENT

9.1. Sequence Generation

When a potentially eligible person with a RRD is identified, they will be informed about the COMBAT study. If they are willing to take part, informed consent will be obtained, and eligibility confirmed. If eligible, the baseline visit (see Data Collection section, below) will be undertaken (as soon as possible and before the surgery) and participants will be randomised (1:1) to receive phacovitrectomy or vitrectomy. An automated system with the allocation concealed to the ophthalmologist recruiting the participant will be used to generate the random allocation sequence. A minimisation algorithm will be used to ensure balanced allocation of participants across treatment groups for potentially important factors including centre, surgeon's experience (consultant/vitreoretinal fellow), presenting BCVA (BCVA \geq 69 ETDRS letters [Snellen equivalent \geq 20/40; logMAR \geq 0.3], 24–68 ETDRS letters [Snellen equivalent \leq 20/50-20/320; logMAR 0.4–1.2], \leq 24 ETDRS letters [Snellen equivalent \leq 20/320]); macular status (macula on & fovea on, macula off & fovea on, fovea off \leq 7 days, fovea off 7-14 days, fovea off 15-30 days, fovea off \leq 30 days); and presence/absence of PVR-C.

9.2. Allocation Concealment Mechanism

An automated system will be used to generate the random allocation sequence, which will conceal the allocation from the ophthalmologist.

9.3. Allocation Implementation

Sites will be provided with trial specific randomisation guidelines. Randomisation will be completed by an appropriately trained and delegated member of the research team. Each participant will be allocated their own unique trial identifier during the randomisation process, which will be used throughout the study for participant identification on all data collection forms and questionnaires. The patient's allocation will be provided only to unmasked staff (e.g. the surgeon, theatre team).

9.4. Masking

Optometrists obtaining the primary outcome measure will be masked to treatment allocation. Masked assessors will not have access to clinical information about the participant and only to blank worksheets, which they will be given to record pertinent data. The trial statistician, who has no role in decision-making with regard to the conduct of the trial, will be unmasked. This will facilitate linkage with the DMEC. The remainder of the trial team at the NICTU will be unmasked for the purposes of managing data collection, reviewing cases to assess protocol deviations, and safety reporting. Staff delivering treatments and participants receiving the treatments will not be masked to treatment allocation.

10. OUTCOME MEASURES

10.1. Primary Outcome Measure

Change in Best-Corrected Visual Acuity (BCVA) in the affected study eye from baseline to 52 weeks (+/- 6 weeks) after surgery (equivalence margin +/- 7 ETDRS letters).

10.2. Secondary Outcome Measures

All at 52 weeks (+/- 6 weeks) after surgery for all outcomes except *:

- Primary anatomical success (proportion of eyes with an attached retina after one vitrectomy).
- Final anatomical success (proportion of eyes with an attached retina after two or more vitrectomies).
- Intraoperative complications (total number and by severity score). (18, 19).
- Postoperative complications (total number and by severity score). (18,19).
- Number and type of surgeries performed.
- Refractive error* (difference between aimed (sought) and obtained post-operative refraction
 12 weeks after surgery in the phaco-vitrectomy arm and 6-8 weeks post-cataract surgery, if this takes place, as per standard of care, in the vitrectomy only arm).
- Proportion of participants with BCVA <69 letters
- Proportion of participants with BCVA <34 letters.
- Time to achieve 'best vision'.
- Change in BCVA from baseline over time.
- Health related quality of life measured using EuroQol-5 level (EQ-5D-5L) (20).
- Vision-specific quality of life measured using the National Eye Institute Visual Function Questionnaire-25 (NEI VFQ-25) (21).
- Participant's experience, and acceptability of treatments.
- Use of health and social care services and non-health care costs.
- Safety

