4. BACKGROUND AND RATIONALE

4.1. Background Information

Rhegmatogenous retinal detachment (RRD) is the separation of the retina from the wall of the eye, where it is normally attached. It affects 10-18 people per 100,000 per year (1,2). Thus, in the UK, with a population of around 68 million (3) there are 6700-12,000 RRD per year.

RRD can lead to permanent central and peripheral vision loss (i.e. total blindness) if not treated in a timely manner. Vitrectomy is the most common surgery done for RRD (4,5). Retinal reattachment following one vitrectomy occurs in 80-88% of eyes, with 59-67% gaining vision above 0.3 LogMAR, which is the vision required to fulfil UK driving standards (4,5).

Data from the British and Eire Association of Vitreo-Retinal Surgeons (BEAVRS) showed that most patients with RRD are phakic; this means that they still have their natural lens (i.e. have not had cataract surgery) (5). Data from the BEAVRS database (unpublished, but accessible to the COMBAT

Doc no: Page 12 of 38 Protocol v1.0 Final 25.02.25 IRAS 338079

research group) showed that of 8436 vitrectomies done in non-high myopic phakic eyes out of 13,900 vitrectomies performed at several sites in the UK, only 10% combined vitrectomy with cataract surgery (called phacovitrectomy) at the time of the RRD repair. Of 664 phakic eyes with at least 12 months follow-up in which combined surgery was not performed at the time of RRD surgery, 320 (48%) were recorded to have a cataract or to have had it already removed within three months of the original vitrectomy. Only 20% of these eyes had their own clear natural lens at 12 months following vitrectomy. Therefore, phacovitrectomy is done in a minority of patients at the time of RRD repair; and many patients have either a cataract present or undergo separate cataract surgery soon after the RRD surgery.

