5. STUDY AIM AND OBJECTIVES

5.1. Research Hypothesis

We hypothesise that combined phacovitrectomy will be preferred by patients because it will provide faster visual recovery and obviate the need for a second surgery (the cataract surgery) following RRD repair, and possibly reduce the number of reoperations related to failure to re-attach the retina. The COMBAT PPI Group have highlighted that obviating the need for further cataract surgery should have a positive impact on patients because of the stress and anxiety that occurs before surgical procedures. Phacovitrectomy may reduce the number of visits and admissions to hospital, reducing costs and pressures on the NHS and probably reducing costs to patients such as travel costs and time off work for attending hospital visits. These costs are especially problematic for patients with limited income and the self-employed. Phacovitrectomy may also reduce other health inequalities because if cataract surgery is required after RRD repair, long waiting times for this surgery in the NHS could adversely affect people with lower income who may be unable to achieve visual rehabilitation as quickly as those with higher income who can afford to have their cataracts removed privately.

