12.4. Clinical Outcomes

Best-Corrected Visual Acuity (BCVA)

The primary outcome is change in BCVA from baseline to 52 weeks (+/- 6 weeks) after surgery in the study eye. There is no consensus on the core outcomes to be measured in trials for RRD but BCVA is routinely measured in the standard care of patients with RRD and in ophthalmology trials. It is considered, together with retinal reattachment, as a main outcome of surgical success in clinical practice. BCVA closely relates to patient-reported quality of life. Full-refracted distance BCVA will be measured in both eyes using the ETDRS Visual Acuity charts at 4 meters by masked optometrists/ophthalmologists at baseline and at week 6, 12 and 52 after surgery, following the COMBAT SOP.

Note: If the surgery takes place more than three days after the baseline assessment, or if the patient reports a change in their vision since the baseline assessment, the BCVA should be repeated before the surgery.

Retinal Reattachment

Patients will be evaluated using slit-lamp biomicroscopy with wide angle non-contact or contact lenses and/or indirect ophthalmoscopy, as per standard practice at participating sites, and the status of the retina (fully attached/detached) will be recorded in the appropriate CRF.

Intraoperative and Postoperative Complications

Intra- and post-operative complications will be prospectively recorded using CORDS (The Classification for the Reporting of Complications in Retinal Detachment Surgical Trials) (19), a robustly developed classification of complications of vitreoretinal surgery (18). Complications will be scored as per this classification and analysed. Intraoperative and postoperative complications of cataract surgery will be also recorded.

Furthermore, presence/absence of posterior capsule opacification (PCO) and performance of YAG laser posterior capsulotomy will be prospectively recorded during the trial in the appropriate CRF (Note: surgeons who routinely do posterior capsulectomy at the time of the phacovitrectomy will be allowed to do so in COMBAT, recording this procedure in the pertinent surgical CRF).

Number and Type of Surgeries Performed

The number and type (e.g. surgery for retinal re-detachment – i.e. if surgical failure occurs; cataract surgery; other) of surgeries performed throughout the trial will be recorded in the appropriate CRFs.

Refractive Error

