14.2. Data Analysis

Statistical Methods

As this is an equivalence trial for the primary outcome, the primary statistical analysis will be per protocol, but an intention-to-treat analysis will be also undertaken (30). The difference between randomised groups for change in BCVA (using 95% confidence interval [CI]) from baseline to week 52 post surgery) will be compared to the permitted maximum difference (PMD) of +/-7 ETDRS letters using an analysis of covariance model adjusting for baseline BCVA and minimisation factors. If the 95% CI of the treatment difference lies wholly within both upper and lower margins of the PMD, phacovitrectomy could be deemed equivalent to vitrectomy alone. A 7 ETDRS letter equivalence margin is not considered clinically important and could relate to test re-test variability (28,29).

A secondary analysis from baseline to week 52 post-surgery will be compared to the permitted maximum difference (PMD) of +/-7 ETDRS letters using two one sided 2-sample t-tests.

The primary analysis will use data from the study eye only. Analyses of categorical secondary outcomes will use general linear models (GLM) with adjustment for minimisation covariates. Relative risk, risk difference and odds ratio will be reported where possible. Analyses of continuous secondary outcomes will use ANCOVA adjusting for corresponding baseline and minimisation factors, as appropriate. For time to best vision, we will use two-sample t-test or non-parametric alternative based on distribution of the data. For change in BCVA over time, we will compare the Area Under the Curve between groups. Statistical significance for secondary outcomes will be based on two-sided tests with p<0.05 as the criterion for statistical significance.

The primary outcome will be analysed according to pre-specified subgroups (e.g. surgeon experience [consultant/vitreoretinal fellow]; macula/fovea on/off, presence of PVR-C; number of quadrants of detached retina, presence of inferior breaks in detached retina) by including the corresponding interaction term in the GLM and using 99% confidence intervals.

A sensitivity analyses will be conducted for the primary outcome; looking at change in vision, if surgery takes place more than 3 days after the baseline assessment.

Baseline characteristics, follow-up measurements (including occurrence of cataract surgery) and safety data will be reported using descriptive summary measures depending on scale of measure/distribution.

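### Final anatomical success, read as written, leaves out eyes attached after their first vitrectomy, so it does not measure final attachment and can rank the better arm lower

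*Protocol*

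**What the plan says.** Protocol section 10.2 lists two anatomical outcomes, both under a lead-in that sets the time point at 52 weeks. The first is "Primary anatomical success (proportion of eyes with an attached retina after one vitrectomy". The second, which is the subject of this point, is "Final anatomical success (proportion of eyes with an attached retina after two or more vitrectomies". The key secondary outcomes in section 1 give the same two definitions.

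Section 8.2 allows further surgery for the detachment when the first operation fails, that is "if the retina remains detached or if it attaches but then re-detaches". Section 12.4 says how the finding is captured: "the status of the retina (fully attached/detached) will be recorded in the appropriate CRF". It does not define final success. Section 14.2 sets the analysis: "Analyses of categorical secondary outcomes will use general linear models (GLM) with adjustment for minimisation covariates". It also sets the criterion: "Statistical significance for secondary outcomes will be based on two-sided tests with p<0.05". Neither statement redefines this outcome or names its denominator.

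**The concern.** The two definitions do not overlap: one counts eyes attached after a single vitrectomy, the other counts eyes attached after at least two. An eye repaired at the first attempt and never re-operated therefore falls outside the numerator of an outcome called final success.

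Two denominators can be read into the definition. With all eyes, the score depends mainly on how many first operations failed, and more failures give more room to score. With re-operated eyes only, the comparison is restricted to a group formed by an event after randomisation. Neither gives the proportion of eyes attached at the end of follow-up.

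This matters because the protocol looks for superiority on secondary outcomes. Section 5.1 suggests that phacovitrectomy may "possibly reduce the number of reoperations related to failure to re-attach the retina". If that happens, the literal outcome could count the benefit against the arm that produced it.

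**Working it through.** **Inputs**

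- Single-surgery success, s: section 4.1 states "Retinal reattachment following one vitrectomy occurs in 80-88% of eyes". The two ends of this range serve as an illustrative better arm (88%) and worse arm (80%).
- Re-operation success, r: the protocol gives no figure. Assumed 50% to 100%, first equal in both arms, then unequal.
- Evaluable eyes per arm: from section 14.1 (SD 15.2, margin 7, two one-sided tests at 2.5%, 90% power, 1:1 allocation).
- Second vitrectomies are taken to be done only after failure of the first.

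**Arm size, reproduced first**

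The normal approximation with true difference 0 gives n per arm = 2 × (15.2 × (1.960 + 1.645) / 7)² = 122.6, so 123. With the noncentral t distribution, power is 0.898 at 123 per arm and 0.902 at 124. This gives 248 in total, as stated. Then 248 / 0.90 = 275.6, so 276, also as stated. The illustration uses 124 evaluable eyes per arm.

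**All eyes as denominator**

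Literal score = (1 − s) × r. Cumulative attachment = s + (1 − s) × r.

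The ceiling of the literal score is at r = 100%: 1 − 0.88 = 12% and 1 − 0.80 = 20%. Both lie far below primary success.

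| r, equal in both arms | Literal, s = 88% | Literal, s = 80% | Cumulative, s = 88% | Cumulative, s = 80% |
|---|---|---|---|---|
| 50% | 6.0% | 10.0% | 94.0% | 90.0% |
| 80% | 9.6% | 16.0% | 97.6% | 96.0% |
| 100% | 12.0% | 20.0% | 100% | 100% |

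At r = 80% the literal counts are about 12 and 20 of 124 eyes, and the cumulative counts are 121 and 119. The literal score ranks the better arm lower in every row. The cumulative score ranks it higher, or ties at r = 100%.

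**When the reversal stops**

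The literal scores are equal when 0.12 × r(better) = 0.20 × r(worse), that is r(worse) = 0.60 × r(better). Below that ratio the order is right again. For example, r = 90% in the better arm and 50% in the worse arm give 0.12 × 0.90 = 10.8% and 0.20 × 0.50 = 10.0%.

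**Re-operated eyes as denominator**

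The score is then r itself, so no reversal is built in. The number of eyes is at most 0.12 × 124 = 14.9 to 0.20 × 124 = 24.8 per arm. It is fewer if some failed eyes are not re-operated, since section 8.2 allows further surgery but does not require it.

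**The case against.** The strongest defence is that the wording is loose and the intent is clear. Primary and final success are set against each other, the lead-in in section 10.2 fixes week 52, and section 8.2 provides for further surgery after failure. Together these point to cumulative attachment. The promised statistical analysis plan could set numerator and denominator. No information would be lost either: with all eyes as denominator the two items add up to total attachment (at r = 80%, 88.0 + 9.6 = 97.6 and 80.0 + 16.0 = 96.0), and the surgery count is its own outcome.

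Much of this stands. The intended meaning is probably cumulative, the data needed are collected, and a careful reader of the results table could recover the right figure. That limits the seriousness.

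It does not remove the defect. The definition is not left open for the analysis plan; it is stated, in two places, in words that exclude first-operation successes. An analysis plan that followed it would carry the problem forward, and one that corrected it would contradict the protocol. The literal outcome would also receive its own test at the 5% level.

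A reader might go further and infer that the better arm must score worse. The protocol does not support that. It names no denominator, the reversal needs all eyes in it, and it also needs re-operation success in the worse arm to stay above 0.60 times that in the better arm. Nor does the protocol assert that phacovitrectomy improves first-operation success; section 5.1 puts fewer re-operations only as a possibility.

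**Conclusion.** The definition is wrong as written, under either denominator. With all eyes, it is capped at 12-20% and can reverse the order of the arms: 9.6% against 16.0% where cumulative attachment is 97.6% against 96.0%. With re-operated eyes only, it compares at most about 15-25 eyes per arm in a group that randomisation no longer protects.

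The sizes rest on the background range of 80-88% applied to the two arms, on an assumed re-operation success, and on second vitrectomies following only failed first ones. That literal reading leaves out first-operation successes rests on none of these assumptions.

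This should be corrected before analysis, but it does not threaten the trial. It is one secondary outcome among many, primary anatomical success is separately defined, and the primary outcome, the equivalence decision and the sample size are untouched.

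**What to change.** In sections 1 and 10.2, define final anatomical success as the proportion of study eyes whose retina is attached at week 52, whatever the number of vitrectomies (one or more). State that it is analysed in the same population, and with the same handling of missing data, as the other categorical secondary outcomes. Requiring all randomised eyes in the denominator would not fit the planned available-case analysis unless a rule were added for eyes without a week-52 examination.

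No separate item for the number of vitrectomies is needed, because the number and type of operations is already an outcome. The cost is a change of wording in two places, handled as a protocol modification under section 17.2. No new data are required: the schedule in section 12.1 has a fundus examination at week 52, and section 12.4 already records retinal status and surgeries.
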